9 STUDY PROCEDURES

9.1 Site Selection, Enrollment and Training

9.1.1 Sampling

Sites will be identified using Allergan field-based knowledge among sites where investigators are certified XEN 45 Gel Stent surgeons and are known to have implanted XEN 45 Gel Stent in the time period being studied. All sites identified by Allergan will be approached for participation in the study in the following countries of interest: Austria, Belgium, Germany, Spain and the United Kingdom.

A recruitment mail containing the study summary, the site qualification questionnaire and a reply coupon will be sent to all sites. If the return rate is insufficient, non-responders will be contacted by telephone to fill out the site qualification questionnaire.

Allergan or designee will qualify sites with sufficient resources (time, personnel, and facilities) to participate in the study. Sites will be required to obtain approval from the appropriate Independent Ethics Committee (IEC) as appropriate according to local laws, and will be responsible for maintaining all related documents, before enrollment of any patient into the study.

Recruitment will end once approximately 15 qualified sites have agreed to participate in the study.

9.1.2 Site Initiation

Sites will receive a study kit once all the necessary administrative procedures have been completed (confidentiality agreement, research contract agreement, curriculum vitae... where applicable).

The study kit contains the following:

- Study protocol
- Screening Log
- Electronic case report form (eCRF) user manual.

An initiation telephone call will be organized by Clinical Research Associates (CRA) to explain the protocol, data collection, and the practical aspects of the study.

In addition, designated study personnel will participate in a training program that will encourage consistency of processes and procedures at the investigative sites and ensure collection of high-quality data for this study. All sites will be trained on the protocol, study logistics, and the EDC system. Retraining will be conducted as needed.

9.1.3 Site Monitoring

During the data-extraction period, sites will be contacted by telephone by CRAs to follow the site identification of patients, the eCRF completion and to answer any questions sites may have concerning data to be collected and the logistics of the study. Frequency of telephone calls will be site dependent and based on identified needs for each site. A close out call will be performed by CRAs at the end of the study. Site monitoring processes will be further detailed in the Site Management and Monitoring Plan.

9.2 Patient Identification and Selection Procedures

Medical charts will be screened by the investigative site personnel to identify eyes who satisfy all the inclusion and none of the exclusion criteria. The number of eyes selected at each site will be chosen based on the results of the feasibility assessment and consultations with the Sponsor. Eye selection will not be competitive and will stop when the target number of eligible eyes has been reached.

Once a site has been initiated, site personnel will be invited to complete a screening log with all patients' eyes that underwent XEN 45 Gel Stent implantation from 1 January 2014 until 31 December 2014. Data collected in the screening log, listed in Section 10.1, will help site personnel identify eligible eyes. Upon screening log completion, the sites will proceed through the patients' eyes listed in the screening log and extract data from eyes who meet all the inclusion criteria and none of the exclusion criteria. Consent from patients will not be requested; as the study is retrospective and fully anonymized, a waiver of consent will be requested from the IECs. Sites will proceed chronologically for entry of eligible eyes data in the EDC system, starting with the eligible eyes that underwent XEN 45 Gel Stent implantation the closest to 1 January 2014. Exceptions will be made when sites encounter an eye from a patient with both eyes meeting selection criteria. Once data from the first eye have been extracted, sites will extract data from the second eye, regardless of its XEN 45 Gel Stent implantation date, so that eyes can be paired in the EDC.

Once the charts of all eligible eyes listed in the screening log have been extracted for entry on the eCRF, and if the target number of eyes for the primary analysis has not been reached, site personnel will be invited to complete a new screening log with charts of patients' eyes that underwent XEN 45 Gel Stent implantation in the following 3 months (i.e. between 1 January 2015 and 31 March 2015). This process will be repeated periodically thereafter as applicable until the target number of eyes has been reached.

Sites will make sure that after data have been entered in the study database, there will be no possibility to link the data collected in the screening log or eCRF to a patient name.

10 STUDY ASSESSMENTS

10.1 Data Collected in the Screening Log

Once a site has been initiated, site personnel will be required to complete an anonymized screening log with all patients' eyes that underwent XEN 45 Gel Stent implantation as described in Section 9.2. If both eyes of a patient had undergone XEN 45 Gel Stent implantation, one line should be completed in the screening log per treated eye. For all screened patients' eyes, the data listed in Table 3 will be collected to help site personnel identify eligible eyes.

Table 3 Data Collected in Screening Logs

Data Collected	Selection Criteria
• Eye in which XEN 45 Gel Stent was implanted (OD vs. OS)	N/A
• Indication for XEN 45 Gel Stent implantation	IC1
• Date (MM YYYY) of XEN 45 Gel Stent implantation	IC2
• Date (MM YYYY) of Last Visit ^[a,b]	IC2
• Reason why the patient has not been selected for the study (did not meet selection criteria, lack of time, quotas were met, insufficient access to complete medical records, etc.)	N/A

IC=Inclusion criteria; N/A=not applicable; OD=oculus dexter; OS=oculus sinister

[a]. Last Visit is defined as the date of the last follow-up visit available prior to 1 October 2018 or date on which the patient had a SSI for glaucoma, whichever occurs first.

[b] Automated calculation will be implemented in the screening log to verify whether Last Visit occurred at least 3 years after XEN 45 Gel Stent implantation

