8.2.1 Inclusion Criteria

A patient's eye must meet **all** of the following criteria to be eligible for participation in the study.

1. Eye treated with XEN 45 Gel Stent for open angle glaucoma as a standalone procedure or in combination with phacoemulsification
2. XEN 45 Gel Stent was implanted between 1 January 2014 and 1 October 2015

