8.2.3 Minimum Required Dataset

Medical charts that do not include the following data will not be selected for the study. Therefore, if no data is available within the charts at the study site, before selecting the chart for inclusion in the study it must be established that certain key data from other locations will be made available for investigators for data entry.

Patient characteristics

- Age
- Gender

Intraocular Pressure

- IOP at baseline (i.e. medicated IOP) and until last visit (1 October 2018 or until the date on which the patient received a SSI for glaucoma, whichever occurs first)
- Number of topical IOP-lowering medication prescribed for the study eye at baseline and until last visit (1 October 2018 or until the date on which the patient received a SSI for glaucoma, whichever occurs first)

Secondary surgical intervention

- Date of the SSI for glaucoma, if any

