14 STATISTICAL METHODS

14.1 Sample Size

To answer study primary objective, this chart review study plans to accrue a minimum of 60 study eyes that have had at least 3 years of follow-up data without a SSI for glaucoma after the initial implant with XEN 45 Gel Stent.

Data from the Allergan study MS-001 demonstrated that the mean IOP reduction from baseline differed slightly among the 7 visits (see below) in the 24-month post-implant period. The absence of a clear waning-out trend suggests that the effect of XEN 45 Gel Stent implantation on IOP reduction may last to Month 36 and beyond. The minimum mean reduction (negative sign stands for reduction) in IOP among the visits was -5.6 (± 6.32) mmHg, which was observed at Month 3. This value was then taken as an initial estimate for the mean reduction projected for Month 36. The 95% confidence interval (CI) of the projected mean reduction afforded by a sample of 60 study eyes is -7.2 to -4.0 mmHg. That is, the half-length of the interval is 1.6 mmHg, which provides a reasonable precision for the estimate of the projected mean reduction in IOP.

Table 4 Result from the MS-001 Study

Visit	Number of study eyes	Mean (SD) change in IOP from medicated baseline (mmHg)
Month 1	167	-6.3 (6.41)
Month 3	167	-5.6 (6.32)
Month 6	168	-6.4 (4.92)
Month 9	134	-6.1 (5.68)
Month 12	161	-6.7 (5.41)
Month 18	149	-7.1 (5.10)
Month 24	149	-6.2 (4.94)

The MS-001 study enrolled 199 patients (218 study eyes). In this study, patients' discontinuation rate tended to be linear over the 2-year follow-up period, with an overall study discontinuation rate of approximately 20%. Using data from the MS-001 study, it could be assumed that 30% of the eyes selected for this study have less than 3 years of follow-up data. Taking into consideration that MS-001 study was a clinical trial and that patient retention rate is expected to be lower in a real-world setting, the study will aim to select 150 eyes to ensure obtaining a minimum of 60 eyes with at least 3 years of follow-up data.

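### Table 3 of the protocol labels a 3-year follow-up check as inclusion criterion IC2, which has no follow-up requirement; unless clarified, a site could screen out eyes with an early SSI or early loss to follow-up

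*Protocol*

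**What the plan says.** Table 3 in Protocol 10.1 has a column for the selection criterion that each log field serves. The side of the eye and the reason for non-selection are marked N/A. The date of Last Visit is marked IC2, the same label as the implantation date. Two footnotes hang on that row:

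- Footnote [a]: Last Visit means the final follow-up on record before the cut-off of 1 October 2018 or, if earlier, the day of an SSI for glaucoma.
- Footnote [b]: an automated calculation is built into the log "to verify whether Last Visit occurred at least 3 years after XEN 45 Gel Stent implantation".

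Section 10.1 gives the purpose of the log: "the data listed in Table 3 will be collected to help site personnel identify eligible eyes". Section 9.2 repeats it: "Data collected in the screening log, listed in Section 10.1, will help site personnel identify eligible eyes".

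The criterion itself (Protocol 8.2.1, repeated in SAP 1.7) reads: "XEN 45 Gel Stent was implanted between 1 January 2014 and 1 October 2015". It sets no minimum follow-up. Section 8.2.2 lists no exclusion criteria. The minimum dataset in Section 8.2.3 includes "Date of the SSI for glaucoma, if any", with IOP and medication data needed only up to that date. Section 14.1 plans for short follow-up among selected eyes: "it could be assumed that 30% of the eyes selected for this study have less than 3 years of follow-up data".

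**The concern.** The tool that sites use to decide eligibility carries a test that the eligibility criteria do not contain, under the label of a criterion that says something else. Because Last Visit stops at an SSI, an eye with an SSI at Year 1 fails the test, and so does an eye lost to follow-up before 3 years. The same table offers failure to meet the selection criteria as a reason for non-selection, so a site that takes the label at face value has a ready code for leaving the eye out.

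Selection would then depend on the outcome. The analyses at stake are Kaplan-Meier time to SSI, qualified and complete success, and the summaries of adverse events of special interest (AESIs). The error would be hard to trace. Table 3 has no SSI field, so a short interval to Last Visit looks the same whether the cause was an SSI or ordinary loss. The data are anonymised, and Sections 12 and 14.3.3 rule out queries to sites.

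**Working it through.** **1. The provisions side by side.** Take an eye implanted in the window for open angle glaucoma, with the minimum dataset and an SSI at Year 1.

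| Place | Status of this eye |
|---|---|
| Protocol 8.2.1 and 8.2.2; SAP 1.7 | Eligible: both criteria met, no exclusions |
| Protocol 8.2.3 | Selectable: data needed only to the SSI, and the SSI date is requested |
| Protocol 9.2 and 14.3.2 | To be extracted in chronological order with all other eligible eyes |
| Protocol 14.1 | One of the eyes with under 3 years that the plan expects |
| Protocol 14.2.5.2; SAP 4.4.1 and 4.6 | An event in the Kaplan-Meier analysis and a failure on the success definition |
| Protocol 10.1, Table 3 | Fails the check shown under IC2 (Year 1 is less than 3 years) |

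Only the last row conflicts with the others.

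**2. The plan's own figures.** Inputs are from Protocol 14.1: about 20% discontinuation over 24 months in MS-001, roughly linear; 150 eyes selected; at least 60 needed with 3 years.

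- Short follow-up at 36 months: 20% × 36/24 = 30%, as stated.
- Expected eyes with 3 years: 150 × 0.70 = 105.
- Shortfall that the plan can absorb: 1 − 60/150 = 60%, or 90 eyes.
- Precision at n = 60: 1.96 × 6.32/√60 = 1.599 mmHg, so −5.6 ± 1.6 gives −7.2 to −4.0, as stated.

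The step from 60 to 150 makes sense only if eyes with short follow-up are selected. With the check as a gate, the share of selected eyes with under 3 years would be 0%, not 30%.

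**3. Effect of a gate on time to SSI.** Let V be the last follow-up visit and T the SSI date, in months from implantation. Last Visit is L = min(V, T). Requiring L ≥ 36 forces T ≥ 36 in every selected eye. The Kaplan-Meier estimate of SSI-free survival at 36 months is then 100% whatever the true rate. The only slack is rounding, because the log holds dates as month and year.

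**4. Effect of a gate on 3-year success.** The documents give no SSI rate, so this is an illustration on assumed inputs. Let f be the share of eyes with an SSI before 3 years and s the success rate among eyes that reach 3 years without one. Assume no other loss, and that SSI eyes stay in the denominator as failures. Success is (1 − f)s in all eyes and s in gated eyes, so the overstatement is f × s.

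| f | All eyes, s = 60% | Overstatement | All eyes, s = 40% | Overstatement |
|---|---|---|---|---|
| 5% | 57% | 3 points | 38% | 2 points |
| 10% | 54% | 6 points | 36% | 4 points |
| 20% | 48% | 12 points | 32% | 8 points |
| 30% | 42% | 18 points | 28% | 12 points |

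**5. What a gate would change little.** Protocol 14.2.4 already limits the Year 3 IOP and medication analysis to eyes with at least 3 years of follow-up. The proportions with a 20% reduction or an IOP below a threshold already leave out SSI eyes (Protocol 14.2.5.2, SAP 4.4.1).

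**The case against.** The best defence is that the check is a counter. Section 9.2 opens a further screening log only while the primary-analysis target is unmet. Section 14.1 defines that target as 60 eyes with at least 3 years of follow-up and no SSI. Because Last Visit stops at an SSI, footnote [b] computes exactly that condition. The IC2 label may simply reflect that the implantation window closes on 1 October 2015, exactly 3 years before the data cut-off. Sites are trained on the protocol and followed by telephone, and Section 14.3.2 compares selected with non-selected eyes.

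Much of this stands. Counting is a plausible purpose and fits Sections 9.2 and 14.1 better than a gate does. A reader might infer from Table 3 that the protocol requires 3 SSI-free years for entry. It does not: footnote [b] asks for verification, no text says a failing eye is left out, and the operative criteria point the other way.

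A reader might also infer that a gate would remove every SSI failure from Month 36 success. That is too strong. The SAP 4.1 window runs to Month 39, so an eye with an SSI at Month 37 passes the check.

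Two things remain. The counting purpose is written nowhere, while the table marks other non-selection fields N/A and this one IC2. And the comparison in Section 14.3.2 could reveal that eyes with short follow-up were left out, but it could neither prevent this nor separate SSI from other loss.

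**Conclusion.** The point holds as an internal inconsistency in the selection tool, with a conditional consequence. If a site applies the check as labelled, eyes with an SSI or loss before 3 years are left out. SSI-free survival at 36 months then becomes 100% by construction for that site's eyes, and qualified and complete success and the AESI results are biased. If sites treat the check as a counter, there is no harm.

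The size of the bias cannot be stated, because the documents give no SSI rate and no indication of how sites read the label. The overstatements of 2 to 18 points above rest wholly on assumed inputs.

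A reader might multiply 30% by 150 and conclude that 45 eyes would be lost. The documents do not support that as an estimate or a bound. The 30% extrapolates discontinuation in a clinical trial and is not an SSI rate. Section 14.1 expects poorer retention in practice, and the plan can absorb 90 short eyes among the 150.

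**What to change.** 1. In Protocol Table 3, change the selection-criterion entry for the Last Visit row from IC2 to N/A.
2. Add to footnote [b]: *This calculation only counts eyes toward the target of 60 for the primary analysis. It is not a selection criterion.*
3. Add to Section 9.2: *Eyes that meet IC1, IC2 and the minimum dataset are eligible and must be extracted in chronological order, including those with an SSI for glaucoma or less than 3 years of follow-up.*

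The cost is one edit to the log template and two or three sentences. No stated figure changes: at the plan's 30%, 150 eyes still give 105 with 3 years, and the precision at 60 eyes is unaffected. Hiding the flag from sites would add little, since both dates sit in the same log and the stopping rule in Section 9.2 needs the count.

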10.2 Demographics

Patients' age at implantation of XEN 45 Gel Stent, gender and race will be recorded in the eCRF.

Selected eye characteristics (OD vs. OS), along with information about whether patient's other eye was also selected will be collected.

10.3 Ocular and Glaucoma Medical History

Ocular history of the selected eye will be collected, such as glaucoma diagnosis, previous ocular and glaucoma procedures, previous ocular medications (including whether or not eye is treated with Diamox on the day when decision was taken to implant XEN 45 Gel Stent) and ocular pathologies observed at baseline. Glaucoma stage at baseline will be determined by investigators based on visual field assessment.

10.4 Surgery-Related Data

Use of anti-metabolite and/or anti-fibrotic, procedure performed (i.e., XEN 45 Gel Stent implantation alone or phacoemulsification + XEN 45 Gel Stent implantation), XEN 45 Gel Stent and cataract-related complications, and, if available surgical, notes will be collected.

10.5 Intraocular Pressure Data

IOP-related data, i.e. IOP and number of IOP-lowering medications, will be collected at the visit when the decision was made to implant XEN 45 Gel Stent, and not the day of implantation. IOP-related data will also be collected for all data collection points defined for the study period.

10.6 Eye Assessments

10.6.1 Visual Field Exam

Mean deviation expressed in decibels will be collected at baseline and at all data collection points defined for the study.

Note: If no visual field exam is available at baseline, a value measured up to 12 months prior to baseline is acceptable. In the event that more than one value is available in this 12-month period, the value closest to the baseline date will be used.

10.6.2 Best Corrected Visual Acuity

BCVA in the study eye will be collected at baseline and at all data collection points defined for the study. Values will be recorded in the eCRF according to local practice (Snellen, LogMAR, EDTRS, etc.) along with scale name or method used to assess BCVA.

10.7 Needling Procedures

Date of needling procedures performed on the bleb after XEN 45 Gel Stent implantation will be collected throughout the study period.

10.8 Secondary Surgical Intervention

If a SSI for glaucoma was performed on the study eye during the study period, the nature and date of the SSI will be collected. SSIs for glaucoma include but are not limited to trabeculectomy, table shunt, second gel stent, i-Stent, GATT, ABiC, and transscleral cycloablative procedures.

10.9 Safety Assessments

10.9.1 Definitions

The investigators will classify the adverse event based on the following definitions according to ISO 14155 (2011).

Adverse Event (AE)

Any untoward medical occurrence, unintended disease or injury, or untoward clinical signs (including abnormal laboratory findings) in subjects, users or other persons, whether or not related to the investigational medical device.

Serious Adverse Event (SAE)

An adverse event that:

- a) led to death,
- b) led to serious deterioration in the health of the subject, that either resulted in
 - 1) a life-threatening illness or injury, or

- 2) a permanent impairment of a body structure or a body function, or
 - 3) in-patient or prolonged hospitalization, or
 - 4) medical or surgical intervention to prevent life-threatening illness or injury or permanent impairment to a body structure or a body function,
- c) led to fetal distress, fetal death or a congenital abnormality or birth defect

Note: Planned hospitalization for a pre-existing condition, or a procedure required by the clinical investigation plan, without serious deterioration in health, is not considered a serious adverse event.

Device Malfunction/Failure – Device Specific Events

A device specific event is any malfunction of the device, related or not to the device, resulting or not in the patient undergoing undesirable or harmful experience, that occurs in relation with the conduct of the study.

Device malfunction means the failure of a device to meet its performance specifications or otherwise perform as intended. Performance specifications include all claims made in the labeling for the device. The intended performance of a device refers to the intended use for which the device is labeled or marketed.

Device malfunction may or may not result in the subject experiencing a harmful effect.

All AEs/SAEs associated with a device failure are by definition device related.

10.9.2 Collection and reporting of Safety Events by Investigators

Considering that study aims to explore occurrence over the long term of adverse events identified during clinical studies, this study will collect only the following AESIs:

- Anterior chamber defects:
 - Shallow with peripheral iridocorneal touch
 - Flat with irido-corneal touch extending to the pupil
- Bleb leak
- Blebitis
- Choroidal effusion, hemorrhage or mixed effusion hemorrhage recorded as follows:
 - Extending posterior to the equator, without blood
 - Extending posterior to the equator, with blood
 - Obscuring disc or macula, without blood
 - Obscuring disc or macula, with blood
 - With choroids touching in the center of the eye, without blood
 - With choroids touching in the center of the eye, with blood
- Corneal decompensation (transient i.e. <30 days or persistent i.e. >30days)
- Endophthalmitis
- Hyphema

- ≥ 2 mm in height (layered) at any time
- Present or arising > 30 days postoperatively
- Persistent hypotony: IOP < 6 mmHg, present at two consecutive visits postoperatively > 30 days apart
- Clinical hypotony: vision reduction (2 lines or more) related to macular changes consistent with hypotony maculopathy (macular folds), optic disc edema, and/or serious choroidal detachments because of low IOP
- Implant blockage
- Implant exposure or extrusion / conjunctival erosion
- Implant migration
- Implant repositioning requiring surgical intervention
- Implant touching iris or cornea
- Iritis (requiring treatment after the postoperative medication taper)
- Macular edema
-
- Retinal detachment
- Suture abscess or other local infection
- Vitreous hemorrhage
- Any other adverse event that leads to permanent visual impairment or requires surgical or medical intervention to prevent permanent visual impairment

Due to the retrospective design of the study, the reporting of safety events to the sponsor is not solicited for this study. AEs occurring outside of the data collection period 01 January 2014 to 01 October 2018 are not within the scope of this study and will not be collected. However, should any AEs occur that are outside of this range, Investigators are reminded of the requirement for unsolicited AE reports to be submitted directly to Allergan's Product Surveillance.

